6. ANALYSES AND SUMMARIES

All analyses will be conducted within the SAS population. Analyses will be descriptive in nature. No formal interim analyses are planned.

6.1. Disposition of subjects and Withdrawals

The numbers and percentage of subjects randomized, completing, and withdrawing, along with reasons for withdrawal, will be tabulated, overall and by treatment group.

6.2. Baseline Summaries

All demographic, baseline characteristics and pre-treatment conditions will be summarized using the safety population. Descriptive statistics, including number of patients, mean, standard error, median, and range for continuous variables, and frequency and percent for categorical variables, will be provided for all demographic, baseline characteristics, and pre-treatment conditions.

6.3. Efficacy Analyses

No formal efficacy or outcomes analyses will be performed for this study. However data on the YMRS, CGI-S and CGAS will be summarized using descriptive statistics as described above.

6.4. Special Safety Analyses

No formal analyses for special safety assessments will be performed for this study. However data on the C-SSRS, CDRS-R and Movement disorder scales (SARS, BAS, AIMS) will be summarized using descriptive statistics as described above.

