7.3. Special Safety Assessments

7.3.1. Child Depression Rating Scale – Revised (CDRS-R)

The Child Depression Rating Scale – Revised¹¹ (CDRS-R) is a clinician-rated scale that assesses 17 distinct symptom areas to derive an index of depression severity. Though originally developed for children 6-12 years of age, it has been widely used with adolescents and its developers recommend it for both children and adolescents.¹² Clinicians' ratings are based on information obtained from interviews with both child and parent (or guardian) informants; interview guides have been developed to structure the interview to ensure all 17 symptom areas are assessed. For this trial, the manual's recommendations on resolving discrepancies between informants will be used (ie, most impaired rating given by valid informant will be assigned). It takes about 20-30 minutes to administer and rate the CDRS-R. Ratings are assigned on a 7-point scale (ranging from 1-7, with higher values indicating greater impairment). A total scale score is calculated by summing the 17 items. The total score on the CDRS-R will be used as a safety measure to monitor subjects for the onset of a depressive episode. The CDRS -R will be completed at every visit except baseline (Baseline data will be carried over from Study A1281198).

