7.3.2.3. Abnormal Involuntary Movement Scale (AIMS)

The Abnormal Involuntary Movement Scale¹⁵ (AIMS) will be used to document occurrences of dyskinesias in subjects, specifically tardive dyskinesia. The scale incorporates observation and brief examination of the subject by the investigator and consists of 12 items. Items 1-4 assess the severity of orofacial movements. Items 5-7 assess extremity and truncal dyskinesias. Items 8-10 rate global severity of movements as indicated by the examiner's judgment of the severity of abnormal movements (item 8), the examiner's judgment of the subject's incapacitation due to the movements (item 9), and the subject's awareness of the movements and associated distress (item 10). Items 11-12 concern the subject's dental status.

Items 1-10 are rated on a 5 point (0-4) anchored severity scale with 0 = none, 1 = minimal, may be normal, 2 = mild, 3 = moderate, and 4 = severe. Items 11 and 12 are questions with yes/no answers. Only the sum of the first 7 items will be analyzed. The AIMS can be completed in 5-10 minutes.

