5.2. General Methods

As this is an open label study with no comparator, no inferential statistics will be performed. Quantitative variables will be described by standard descriptive statistics (n, mean, standard deviation, minimum, and maximum, 95% confidence intervals), and qualitative variables will be summarized by frequency tables. Summaries will include data for all subjects who took at least one dose of investigational product in this open label extension study.

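### SAP 6.4 plans no count of subjects whose CDRS-R, SARS, BAS or AIMS scores worsen, so the output will not show how many did

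*SAP*

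**What the plan says.** SAP 6.4 covers the special safety scales in one operative sentence: "data on the C-SSRS, CDRS-R and Movement disorder scales (SARS, BAS, AIMS) will be summarized using descriptive statistics as described above". The reference back is to SAP 5.2, which has two rules:

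- "Quantitative variables will be described by standard descriptive statistics", listed there as n, mean, SD, minimum, maximum and 95% confidence intervals.
- "qualitative variables will be summarized by frequency tables".

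The protocol gives at least two of the scales a purpose at the level of the individual subject. In Protocol 7.3.1 the CDRS-R total "will be used as a safety measure to monitor subjects for the onset of a depressive episode". In Protocol 7.3.2.3 the AIMS is used "to document occurrences of dyskinesias in subjects, specifically tardive dyskinesia". Protocol 7.3.2.1 and 7.3.2.2 use SARS for parkinsonian symptoms and BAS for akathisia.

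Elsewhere the SAP does count subjects. SAP 6.5.6 gives the incidence of categorical QTc increases, and SAP 6.5.4 gives frequency tables around a 1-point rise in BMI z-score. SAP 4.1 requires summaries for Ziprasidone/Ziprasidone, Placebo/Ziprasidone and both combined. SAP 3.4 sets the baseline for these scales at the final visit of the double-blind study.

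**The concern.** Safety and tolerability is the study's only objective, and Protocol section 2 lists these scales under the primary endpoints. The harms they track (a depressive episode, akathisia, dyskinesia) would be expected as a sizeable change in a few subjects, not a small change in everyone. The natural question is how many subjects got worse, and by how much.

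The planned statistics describe the group. A few large rises move a mean very little, and on CDRS-R modest improvement in the remaining subjects can offset them. Neither SAP 6.4 nor SAP 5.2 says that change from baseline will be summarised for these scales, and no worst post-baseline value is defined. A reader of the study report could see that somebody scored high, but not how many did or whether the scores were new.

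**Working it through.** The plan states no figure for this point, so there is none to reproduce. The check asks what the planned statistics can and cannot reveal.

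**Inputs from the documents**
- Expected entrants: 55 (Protocol 9.1).
- CDRS-R total: 17 items scored 1 to 7, so 17 to 119 (Protocol 7.3.1).
- SARS total: 10 items scored 0 to 4, so 0 to 40 (Protocol 7.3.2.1).
- BAS: only the global item, 0 to 5, is analysed (Protocol 7.3.2.2).
- AIMS: only the sum of items 1 to 7, each 0 to 4, is analysed, so 0 to 28 (Protocol 7.3.2.3).

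**Assumed inputs (illustration only).** The numbers of worsening subjects and the sizes of the changes below are not in the documents. The CI is mean ± t × SD/√n, with t(54) = 2.005 and √55 = 7.416.

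**1. Do minimum and maximum fix the count?** Take two sets of 55 BAS global scores, written as numbers of subjects at scores 0, 1, 2, 3, 4, 5.

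| | Set A | Set B |
|---|---|---|
| Subjects at 0–5 | 36, 15, 0, 0, 4, 0 | 42, 0, 9, 3, 1, 0 |
| Sum of scores | 15 + 16 = 31 | 18 + 9 + 4 = 31 |
| Sum of squares | 15 + 64 = 79 | 36 + 27 + 16 = 79 |
| Mean | 31/55 = 0.564 | 0.564 |
| SD = √[(79 − 31²/55)/54] | 1.067 | 1.067 |
| Minimum, maximum | 0, 4 | 0, 4 |
| Subjects scoring 2 or more | 4 | 13 |

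Every statistic planned for a quantitative variable is identical, including the CI, yet the counts differ by 9.

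**2. BAS change, if change were summarised.** Suppose 3 of 55 subjects move from 0 to 3 and the rest do not change.
- Mean = 9/55 = 0.164.
- SD = √[(27 − 9²/55)/54] = 0.688.
- 95% CI = 0.164 ± 2.005 × 0.688/7.416 = −0.02 to 0.35.
- A count would read 3/55 = 5.5% (exact 95% CI 1.1% to 15.1%).

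**3. CDRS-R change, if change were summarised.** Suppose 5 of 55 rise by 25 points and 50 fall by 3.
- Mean = (125 − 150)/55 = −0.45.
- SD = √[(3125 + 450 − 25²/55)/54] = 8.12.
- 95% CI = −0.45 ± 2.005 × 8.12/7.416 = −2.65 to 1.74.
- A count would read 5/55 = 9.1% (exact 95% CI 3.0% to 20.0%), while the mean shows slight improvement.

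**4. Smaller denominator.** With 35% dropout, 55 × 0.65 = 35.75, about 36. Three BAS worseners then move the mean by 9/36 = 0.25, and the count reads 3/36 = 8.3% (1.8% to 22.5%). Dilution is less, but the count is still not recoverable from the planned statistics.

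**The case against.** A reader might infer that the plan reports nothing but means, that it cannot reveal onset at all, or that these scales are the only way such harms are captured. The documents do not support any of these.

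- **Extremes are planned.** The BAS maximum would show the 3 in example 2. If change were summarised, the CDRS-R maximum would show the 25-point rise in example 3.
- **BAS is not classified.** The SAP does not say whether the single 0–5 global item is quantitative or qualitative. A frequency table by score fits the text and would separate sets A and B. It would still not show who moved up from baseline.
- **There is an adverse event route.** Protocol 7.3.2 calls for an adverse event when a clinically meaningful movement disorder is observed or volunteered, when one present at baseline worsens, or when treatment for one is started or reinstated. Dystonic movements are recorded unless unchanged in severity from baseline. SAP 6.5.1 tabulates incidence by system organ class, displays it by severity and attribution, and lists all events.
- **Depression has indirect routes.** The general adverse event definition in Protocol 8.2.1 covers clinically significant symptoms. Needing an antidepressant leads to withdrawal under Protocol 6.4, and SAP 6.1 tabulates reasons for withdrawal. Monitoring for onset can also be read as the clinician's task at each visit, not as a promised incidence endpoint.
- **The change examples are constructed.** They assume a summary of change that neither document states for these scales. The study tests no hypothesis, so a CI that includes zero carries no formal conclusion. Offsetting by improvement is also limited on SARS, BAS and AIMS, where a subject at 0 cannot improve.

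All of this stands, and it makes the gap partial. It does not close it. The adverse event route rests on investigator judgement, and the specified incidence table is by system organ class. Under SAP 6.5.1, an event already seen in the double-blind study is not treatment emergent unless its severity increased. None of these outputs gives the number of subjects whose scale score rose.

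**Conclusion.** The point holds as a partial gap. For CDRS-R, SARS, BAS and AIMS, the SAP does not specify any count of subjects who worsen, and the planned statistics cannot supply one. Example 1 shows this exactly, on the assumption that BAS is treated as quantitative. The same logic applies to the three summed scores, which are plainly numeric. Examples 2 and 3 rest on assumed counts and changes. They show what could happen, not what is expected.

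The gap is largest for CDRS-R, because Protocol 7.3.1 gives it a monitoring purpose but no rule linking a score to an adverse event. It is smaller for the movement scales, which have such a rule. The documents do not support saying that the plan would hide marked akathisia, since an event of that kind should reach the adverse event tables. This is a cheap improvement to the main safety output, not a flaw that undermines the study.

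**What to change.** Add to SAP 6.4, for each prior-treatment group and combined:

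1. **BAS global item:** a shift table from the SAP 3.4 baseline score (0–5) to the worst post-baseline score (0–5).
2. **CDRS-R total, SARS total and AIMS items 1–7 sum:** the number and percent of subjects by size of worst post-baseline increase from the SAP 3.4 baseline, as a cumulative distribution or in fixed-width bands. This needs no outside cut-off. If a single cut-off is also wanted, fix it before database lock.
3. Keep the planned descriptive statistics alongside.
4. Footnote that in the Ziprasidone/Ziprasidone group the baseline was taken on drug. The tables there show further worsening in the extension, not worsening since ziprasidone was first started.

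The cost is a few sentences of SAP text and a few extra tables from data already collected. No new visits or assessments are needed.

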6.5. Safety Analyses

No formal statistical analysis will be conducted on any of the below safety data.

The safety assessments include:

- *Adverse event reporting;*
- *Clinical laboratory testing;*
- *Physical examinations;*
- *Blood pressure and pulse;*
- *Height and weight;*
- *Body Mass Index (BMI) and BMI Z score;*
- *Waist circumference;*
- *Electrocardiograms, including QTc.*

6.5.1. Adverse Events

All randomized subjects who receive at least one dose of antipsychotic treatment will be included in the safety data summarization. All treatment emergent adverse events that are observed from the time of first dosing with open label investigational product until the end of study participation will be included in data summaries. All causality discontinuations and treatment emergent discontinuations from the study will be summarized.

An adverse event is considered treatment emergent relative to a given treatment if:

- the event occurs for the first time during the time of first dosing with open label investigational product until the end of study participation and was not seen prior to the start of treatment in open-label extension (for example, during the baseline or double-blind study), or

- the event was seen prior to the start of treatment but increased in severity during treatment.

All adverse events will be coded according to the Medical Dictionary for Regulatory Activities. The incidence of treatment emergent adverse events will be tabulated by system organ class. The incidence of treatment emergent adverse events will be displayed by severity and attribution. In addition, the incidence of serious adverse events and adverse events that cause withdrawal will be tabulated. All adverse events will be listed.

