9.3. Safety Analysis

The safety assessments include:

- Adverse event reporting, [including Possibly Suicide Related Adverse Events (PSRAEs)];
- Clinical laboratory values;
- Physical Exams;
- Vital signs (blood pressure, pulse rate);
- Weight, height, BMI, BMI Z-score, waist circumference;
- Electrocardiograms;
- No formal statistical analysis will be conducted on any of the above safety data.

Data for height, weight, BMI, and waist circumference will be summarized by time point using descriptive statistics. Additionally, height, weight, and BMI will be standardized using CDC (Child Development Chart) growth charts and the resulting z scores presented in

listings and frequency tables in 1 unit intervals. In addition, frequency tables of above/below a 1 point increase in the z scores for BMI will be presented.

All randomized subjects who receive at least one dose of antipsychotic treatment will be included in the safety data summarization. All adverse events that are observed from the time of first dosing with open label investigational product until the end of study participation will be included in data summaries.

All adverse events will be coded according to the Medical Dictionary for Regulatory Activities. The incidence of treatment emergent adverse events will be tabulated by system organ class. The incidence of treatment emergent adverse events will be displayed by severity and attribution. In addition, the incidence of serious adverse events and adverse events that cause withdrawal will be tabulated. All adverse events will be listed.

All clinical laboratory data will be displayed in listings grouped by type of laboratory test (eg, hematology, blood chemistry) for each sample collection date. Values outside of the normal range will be noted; the respective normal high or low value will be presented in parentheses, linked to the abnormal laboratory value. Laboratory values will be summarized as median changes from baseline and also by frequency of occurrence of clinically significant abnormal values.

All vital sign measurements will be displayed in listings by subject for each sample collection date and time.

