2.1. Study Design

This 26 week open label extension study is designed to provide information on the safety and tolerability of oral ziprasidone (20 to 80 mg BID with meals) during long term administration in children and adolescents with Bipolar I Disorder (current or most recent episode manic). It will enroll subjects who have participated in the 4 week, double blind, placebo controlled safety and efficacy trial, Study A1281198, meet study entry criteria, and wish to receive treatment with open label ziprasidone.

The number of subjects entering this open-label trial will be determined by the number of subjects electing to continue treatment after completing or withdrawing from the preceding double blind Study A1281198. We estimate that approximately 55 subjects randomized in the double blind study (based on the increased sample size of N=194 subjects) will be eligible to continue in this open label extension. With an expected dropout rate of approximately 35%, this gives an estimate of approximately 40 subjects to complete this 26 week open label study (if all 55 subjects enter the extension study).

The final visit of the double blind trial (Week 4 or early termination visit from A1281198) will serve as the Baseline Visit for the extension study. The first 1-14 days of Study A1281201 will be considered a transition period during which the study drug will continue to be administered under double-blind conditions. During this double-blind transition period, subjects who were on placebo in Study A1281198 will be provided active medication that will allow them to be titrated up to the appropriate weight-adjusted target dose, following titration schedule that was employed in Study A1281198. Subjects who were on active medication (ziprasidone) at the end of Study A1281198 will continue on that treatment course under double-blind conditions. At the end of the double-blind transition period, all subjects will receive open label ziprasidone.

Any subject who cannot tolerate the transition study medication during Week 1 should be discontinued from the study.

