After the Week 2 visit for the ≥ 45 kg subjects and after the Week 1 visit for the <45 kg subjects, dosing will be open label and flexible, with dosing adjustments made at the discretion of the investigator to maintain optimal efficacy and tolerability. For subjects with a body weight of ≥ 45 kg, the target dose range is a total daily dose of 120-160 mg/day given in two divided doses with food. For subjects with a body weight <45 kg, the target dose range is a total daily dose of 60-80 mg/day given in two divided doses with food.

Subjects who cannot tolerate a dose of 80 mg/day will be allowed to have a dose reduction and to continue study treatment at a lower dose that is tolerable to them. The minimum permitted dose is 40 mg/day (20 mg BID) for all subjects.

Post Baseline visits will occur at Weeks 1, 2, 4, 6, 10, 14, 18, 22 and 26 during treatment, with a follow up visit at Week 27.

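### SAP 6.5.1 and protocol 9.3 start the adverse event summaries at the first open-label dose, which by the documents' own usage follows the blinded transition; Day 1 is the likely intent and should be stated as the single anchor.

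*SAP*

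**What the plan says.** **Start of the window.** SAP 6.5.1 includes emergent events "observed from the time of first dosing with open label investigational product until the end of study participation". Its first bullet repeats that window for first occurrences. Protocol 9.3 has the same rule: "All adverse events that are observed from the time of first dosing with open label investigational product until the end of study participation".

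**End of the look-back.** The first bullet also requires that the event "was not seen prior to the start of treatment in open-label extension (for example, during the baseline or double-blind study"). The second bullet admits a case where "the event was seen prior to the start of treatment but increased in severity during treatment", with no statement of which treatment start is meant.

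**What open label means.** SAP 2.3 and protocol 5.1 say that open-label product is given for most of the study and name the dose transition as the double-blind exception. SAP 2.1 adds: "At the end of the double-blind transition period, all subjects will receive open label ziprasidone". It places the change after the Week 2 visit for subjects of 45 kg or more; "after the Week 1 visit for the <45 kg subjects, dosing will be open label and flexible". Protocol 5.4.2 dates the first open-label card for the heavier group at Day 15.

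**Who is counted.** The Safety Analysis Set (SAP 4.1) takes anyone with at least one dose of study medication in the extension, so transition dosing qualifies.

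**The concern.** The definition uses two start dates that differ by the length of the transition, and the denominator follows the earlier one. A programmer who looks up the term in SAP 2.3 would start the emergent window at about Day 8 or Day 15.

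Long-term safety and tolerability is the only objective, and adverse event reporting is the first safety endpoint listed in SAP 3.3. On the literal rule, the Placebo/Ziprasidone column would omit the days on which these subjects first receive ziprasidone under the study and are titrated. Ziprasidone/Ziprasidone subjects are already exposed when they enter, so the two columns that SAP 4.1 sets side by side would be affected differently.

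Early stopping is foreseen: "Any subject who cannot tolerate the transition study medication during Week 1 should be discontinued from the study". Such a subject would stay in the denominator without ever having an emergent window.

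**Working it through.** **1. Length of the gap.** Treatment lasts 26 weeks: 26 × 7 = 182 days. The transition lengths come from SAP 2.3.

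| Weight group | Transition | First open-label day | Days outside the literal window | Share of treatment |
|---|---|---|---|---|
| 45 kg or more | Weeks 1 and 2 | 14 + 1 = Day 15 | 14 | 14/182 = 7.7% |
| Under 45 kg | Week 1 | 7 + 1 = Day 8 | 7 | 7/182 = 3.8% |

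Day 15 agrees with protocol 5.4.2. With a Day 1 anchor, the window covers 182 of 182 days in both groups.

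**2. The 14 days are nominal.** Protocol 5.4.2 gives the second transition card only if needed. Protocol 5.6, item 2, allows dose adjustments from Week 2 of the transition and makes them with open-label cards. A heavier subject given such a card in Week 2 could start open-label product near Day 8, with a gap of about 7 days (3.8%). These two passages do not sit easily with protocol 5.1, the Day 15 statement in protocol 5.4.2 and SAP 2.1, and they must be reconciled.

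**3. What the gap contains for former placebo subjects** (placebo titration cards, protocol Tables 1 to 4).

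- 45 kg or more: 20, 40, 40, 60, 60, 80, 80 mg on Days 1 to 7, then 100, 100, 120 mg on Days 8 to 10. All six dose levels fall within 14 days. Four of the six (20 to 80 mg) fall within 7 days.
- Under 45 kg: 20, 40, 40, 40, 60 mg on Days 1 to 5. All three levels fall within 7 days.

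**4. Classifying an event first seen in the transition, read literally.**

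- First bullet: the first occurrence is before the first open-label dose, so it is outside the window. The bullet is not met.
- Look-back: the event occurred after extension treatment began, so it is not a prior event either.
- Second bullet: this needs an event seen before the start of treatment. If that start is Day 1, the bullet is not met; the text does not settle which start applies.

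The event is therefore in neither period and is not treatment emergent.

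**5. Scale of the effect.** The protocol expects about 55 entrants, so each subject missed moves Combined incidence by 1/55 = 1.8 percentage points. The documents give no event rates. As an assumption only, let the onset rate in the transition be k times the later rate. The share of onsets outside the window is then 14k/(14k + 168) or 7k/(7k + 175):

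- k = 1: 7.7% or 3.8%
- k = 3: 42/210 = 20.0% or 21/196 = 10.7%
- k = 5: 70/238 = 29.4% or 35/210 = 16.7%

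These are shares of onsets, not changes in subject incidence.

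**The case against.** The strongest reply is that the documents already point to Day 1. For former placebo subjects, protocol 9 puts the safety baseline before dosing starts in the open-label extension study, normally at the last double-blind visit. SAP 3.4 sets the extension baseline, other than for ECG, at that same visit. The Safety Analysis Set, the schedule's column heading and the heading of protocol 6.2 also treat the whole extension as open label. This stands: Day 1 is probably what was meant, and the window wording is the outlier.

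The consequences are also limited. Events are collected from consent (protocol 8.1.4), all are listed, and SAP 6.5.1 says that "the incidence of serious adverse events and adverse events that cause withdrawal will be tabulated", with no emergence condition in that sentence. A Week 1 withdrawal for an adverse event should therefore still reach a table. No hypothesis or decision rule depends on the window.

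Neither argument removes the conflict. A rule that will be programmed should not rest on inferred intent when the SAP gives the term another meaning.

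Three stronger readings are tempting and are not supported:

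- *Transition events become prior events and count only if they worsen.* That replaces the look-back anchor that the SAP states. Its examples are the baseline and the double-blind study, which in these documents means A1281198; Weeks 1 and 2 are called the transition.
- *Early safety data are lost.* Collection and listing are unaffected.
- *Excluding non-worsening events first seen in A1281198 is an error.* It is an explicit and defensible choice.

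**Conclusion.** The concern holds as a conflict of anchors. SAP 6.5.1 and protocol 9.3 open the window at a dose that, by the documents' usage, follows the transition, while the look-back and the analysis set start from the first extension dose.

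On the literal reading, the emergent tables miss nominally 14 of 182 days (7.7%) at 45 kg or more, or about 7 days where an open-label card is issued in Week 2, and 7 of 182 days (3.8%) under 45 kg. For Placebo/Ziprasidone subjects, that includes first ziprasidone exposure under the study and all or much of the titration. On the Day 1 reading, which is the likely intent, the loss is zero.

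The day counts follow from the documents. The number of events affected does not, and the multiples of the onset rate are illustrations only. A reader might infer that the sponsor means to leave the titration out of the safety tables; the baseline and analysis-set text point the other way. Severity is minor to moderate.

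**What to change.** Use one anchor, the first dose of study medication in A1281201 (Day 1, including the double-blind transition), in the first paragraph and both bullets of SAP 6.5.1 and in protocol 9.3. It should govern the window, the look-back, and the treatment start and treatment period in the second bullet. The rule then reads: an event is treatment emergent if

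- (a) it first occurs from that dose until the end of study participation and was not seen before that dose, including in A1281198; or
- (b) it was seen before that dose and its severity increased from that dose until the end of study participation.

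Separately, reconcile the text on Week 2 cards in protocol 5.4.2 and 5.6 with protocol 5.1 and SAP 2.1. With a Day 1 anchor, the adverse event window no longer depends on the outcome.

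The cost is wording in one SAP section and one protocol sentence, with no new data. Protocol 9 lets the SAP modify the plan but requires an amendment for major changes to the primary endpoint definition or its analysis. This edit secures the likely intent, so the SAP can be corrected now and protocol 9.3 aligned at the next amendment.
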